### **Concomitant therapy**

Prior and concomitant therapies are defined as any medication, and significant non-drug therapies administered to a subject preceding or coinciding with the study assessment period.

Medications will be coded using the World Health Organization (WHO) Drug Reference Listing (WHO DRL) dictionary that employs the WHO Anatomical Therapeutic Chemical (WHO ATC) classification system.

Concomitant therapies will include medications and significant non-drug therapies taken between the first and last day with study medication, excluding medications start on the last day of study medication. Prior therapies will include medications or significant non-drug therapies starting and ending prior to the start of study treatment.

Concomitant and prior therapies will be summarized by ATC class, preferred term and treatment arm for the Safety Set 3 and Safety Set 4. Medications starting prior to the start of study treatment and continuing after the start of study treatment will be counted in both summaries.

All prior and concomitant therapies will be listed.

## **2.7 Baseline**

Baseline is considered as the result of an investigation describing the 'true' uninfluenced state of the patient.

For **efficacy evaluations**, (e.g. serum ferritin), the last available (i.e. non-missing) assessment before or on the date of randomization is taken as 'baseline' value or 'baseline' assessment.

For **safety evaluations** (e.g. laboratory, vital signs, etc.) the last available (i.e. non-missing) assessment before or on the date of start of study treatment is taken as 'baseline' value or 'baseline' assessment.

If patients have no value as defined above, the baseline result will be missing.

If an assessment is planned to be performed prior to the first dose of study drug in the protocol and the assessment is performed on the same day as the first administration of study drug, it will be assumed that it was performed prior to study drug administration, if assessment time point is not collected or is missing. Unscheduled assessments will be considered in the determination of baseline.

Patients who start treatment and discontinue from the study on the same day may have 2 different sets of data collected on study Day 1, one being reported to the week 1 visit, the other reported to the End Of Treatment (EOT) visit. Data reported at the EOT visit are not eligible for baseline selection.

For analyses of the extension phase (entire granule period) requiring comparison to baseline value (e.g. lab shift tables) the baseline is defined as follows. For patients randomized to DT formulation who switched to granule formulation in the extension phase, the last assessment prior or equal to the start date of granules in the extension phase will be defined as pre-granule value which will be reference value for changes in the extension time. For patients randomized to granules continuing in extension phase the initial baseline value at study start will be taken.

## **2.8 Analysis of the primary variables**

The primary objectives of this study are to evaluate patient compliance with study treatment, as measured by the count of deferasirox granule stick packs/dispersible tablets and to evaluate the change in serum ferritin after 24 weeks of treatment for both formulations of deferasirox in pediatric ICT naive patients with iron overload during core phase.

### **2.8.1 Variable**

All analyses for the primary objective will be performed on the FAS-1 and presented by treatment group: deferasirox DT and deferasirox granule formulation.

The co-primary efficacy variables are:

- Compliance measured by stick pack /tablet count based on amount of medication dispensed, returned and reported as lost/wasted by the patient or caregiver in the eCRF, over 24 weeks of treatment (i.e. assessed at week 25 visit). Compliance will be calculated as the ratio of total count consumed to total count prescribed, where
  - total count consumed is derived from cumulative dispensed, returned and lost/wasted counts over 24 weeks of treatment (i.e. assessed at week 25 visit);
  - total count prescribed is derived from cumulative prescribed count over 24 weeks of treatment (i.e. assessed at week 25 visit).

The prescribed count corresponds to the count prescribed by the investigator for the relevant visit period that the patient should have taken during this period. For each strength (125 mg, 250 mg and 500 mg tablets for deferasirox DT; 90 mg, 180 mg and 360 mg tablets for deferasirox granule), the prescribed count for the relevant visit period is calculated from the daily prescribed count at the beginning of this period multiply by the duration (days) of this period. The duration of a period will be calculated as (end date of

the period) – (start date of the period) + 1. The total count prescribed is the sum of counts prescribed per strength.

- Change from baseline in serum ferritin after 24 weeks of treatment (i.e. assessed at week 25 visit).

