Recommended dose adjustment for better treatment effects based on serum ferritin levels and investigator's judgment, will be allowed for ICT naïve patients after 4 weeks of study treatment and for ICT pre-treated patients every 3 months. The dose adjustments will be performed in steps of 5 - 10 mg/kg/day for deferasirox DT or in steps of 3.5 - 7.0 mg/kg/day for deferasirox granules.

During the optional extension phase, dose adjustments in steps of 3.5 to 7.0 mg/kg for deferasirox granules are also only allowed every 3 months.

Dose adjustments based on safety are allowed at any time point in the study. The maximum dose of deferasirox DT will be 40 mg/kg/day and the maximum dose of deferasirox granules will be 28 mg/kg/day.

The starting dose and the dose adjustment considerations must take into account that the therapeutic goal is reduction of iron burden (as opposed to maintenance of iron burden).

The investigator should instruct the patient and/or the legal patient's representative to take the study treatment as prescribed. All doses planned and prescribed to the patient and all dose changes, including the reasons for change, during the study must be recorded in the electronic Case Report Form (eCRF).

During the regular study visits, the investigator or pharmacist will dispense to the patient and/or legal patient's representative, an appropriate number of deferasirox tablets / stick packs depending on the patients calculated dose and Treatment Arm assignment. The number of tablets / stick packs of each strength dispensed will be recorded in the Study Drug Dosing Log. Each time the deferasirox study treatment is dispensed to the patient and/or legal patient's

representative, the investigator will provide detailed instructions on how to prepare and administer the dose. Patients / caregivers will be instructed to take / to administer the assigned amount of study drug and to return all unused study medication including empty stick packs and bottles at their next visit. Study medication returned at each visit will be counted and unused study medication will be recorded by the investigator/ pharmacist involved in the study. Drug accountability will be noted by the field monitor during site visits and at the completion of the trial.

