## **7.2 Assessment types**

### **7.2.1 Compliance with prescribed treatment**

The stick pack/tablet count will be performed by investigator or study personnel every 4 weeks (week 5, 9, 13, 17, 21, 25, 29, 33, 37, 41, 45 and at EOT(core)/777 visits) during the core phase. Assessment of compliance using stick pack/tablet counts will be based on the actual count at the different time points, taking into account the amount of medication dispensed, returned and reported as lost/wasted by the patient in the core phase. Treatment prescribed will be recorded at every visit, including any dose adjustments performed in-between visits. Detailed information related to drug dispensation and returns will be captured in source documents (drug accountability logs) by the investigator or study personnel at each visit during the core phase. During the optional extension phase sites will only collect whether or not the stick pack(s) have been returned from the previous visit.

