### **2.8.1 Variable**

All analyses for the primary objective will be performed on the FAS-1 and presented by treatment group: deferasirox DT and deferasirox granule formulation.

The co-primary efficacy variables are:

- Compliance measured by stick pack /tablet count based on amount of medication dispensed, returned and reported as lost/wasted by the patient or caregiver in the eCRF, over 24 weeks of treatment (i.e. assessed at week 25 visit). Compliance will be calculated as the ratio of total count consumed to total count prescribed, where
  - total count consumed is derived from cumulative dispensed, returned and lost/wasted counts over 24 weeks of treatment (i.e. assessed at week 25 visit);
  - total count prescribed is derived from cumulative prescribed count over 24 weeks of treatment (i.e. assessed at week 25 visit).

The prescribed count corresponds to the count prescribed by the investigator for the relevant visit period that the patient should have taken during this period. For each strength (125 mg, 250 mg and 500 mg tablets for deferasirox DT; 90 mg, 180 mg and 360 mg tablets for deferasirox granule), the prescribed count for the relevant visit period is calculated from the daily prescribed count at the beginning of this period multiply by the duration (days) of this period. The duration of a period will be calculated as (end date of the period) – (start date of the period). The total count prescribed is the sum of counts prescribed per strength. The end date of the period is defined as the date of next assessment.

- Change from baseline in serum ferritin after 24 weeks of treatment (i.e. assessed at week 25 visit).

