#### **2.9.1    Compliance after 48 weeks of treatment during core phase**

Summary statistics of overall compliance measured by stick pack/tablet count assessed at week 48 visit and 95% confidence intervals for means will be provided for FAS-1, FAS-2 and FAS-3. Patient who discontinued before the week 48 visit (end of core phase) will be included in the compliance endpoint calculation. End-of-core visit for patients who continue into extension phase will be calculated based on their last visit before the initiation of treatment of extension phase.

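### The compliance denominator departs from its own definition when an ordered hold or a change in daily count starts or ends inside a visit period

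*SAP*

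**What the plan says.** Compliance over 24 weeks is one of two co-primary endpoints. It is the ratio of total count consumed to total count prescribed (Protocol 10.4.1; SAP Amendment 3, section 2.8.1). The protocol gives no formula for the prescribed count, so the formula is the SAP's own.

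SAP 2.8.1 first describes the prescribed count as the number "that the patient should have taken during this period". It then computes it for each strength as "calculated from the daily prescribed count at the beginning of this period multiply by the duration (days) of this period" and adds the strengths together. The End-of-Core SAP, section 2.8.1, repeats the rule. Neither text splits a period at a dose change or removes days on which the investigator ordered no drug.

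The two SAPs word the period length differently. Amendment 3 ends its formula with "start date of the period) + 1" and gives no period end date. The End-of-Core SAP drops the added day and states: "The end date of the period is defined as the date of next assessment".

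On timing, Protocol 7.2.1 says "The stick pack/tablet count will be performed by investigator or study personnel every 4 weeks", and SAP 4.1.1 has drug dispensed every four weeks. Protocol 6.1.1 says "Dose adjustments based on safety are allowed at any time point in the study". Protocol 7.2.1 adds "Treatment prescribed will be recorded at every visit, including any dose adjustments performed in-between visits", and Protocol 6.2.1 says that accurate adjustment records are needed for this endpoint.

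**The concern.** The formula assumes that the daily count at the start of a period holds to its end, while the protocol provides for changes in between. Table 6-2 includes hepatic holds with weekly liver tests and a 14-day resolution threshold, and a two-week step after rash. With counts 28 days apart, a change lasting 14 days or less cannot both start and end at a counting visit.

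In such a case the consumed count follows the order and the denominator does not. A patient who does exactly as told then gets a ratio other than 100%. The endpoint is meant to measure adherence to the prescription, and to that extent it would measure prescription changes instead. The same variable underlies the 24-week estimates in the primary and End-of-Core reports. It also underlies the 48-week one (End-of-Core SAP 2.9.1: "Summary statistics of overall compliance measured by stick pack/tablet count assessed at week 48 visit"), for which no other denominator is given.

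**Working it through.** **Plan's own figure.** Inputs from SAP 2.11: difference 10 points, SD 17.625, 45 per arm, one-sided 5%, two-group t-test. The noncentral t gives 84.7% power against the stated figure of about 84%, so it reproduces.

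**One patient, ordered hold.** Assume six counting periods of 28 days (6 × 28 = 168 days), one unit a day, full adherence, and one hold of h days that starts and ends inside a period. Under the definition, prescribed = consumed = 168 − h, so the ratio is 100%. Under the formula, prescribed = 168.

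| h (days) | 24 weeks: (168 − h)/168 | Shortfall (points) | Shortfall / 17.625 | 48 weeks: (336 − h)/336 |
|---|---|---|---|---|
| 7 | 95.8% | 4.2 | 0.24 | 97.9% |
| 14 | 91.7% | 8.3 | 0.47 | 95.8% |
| 21 | 87.5% | 12.5 | 0.71 | 93.8% |

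**One patient, change in daily count.** Take a change from 2 units to 1 on day 8 of period 3, then kept. Consumed = 112 + (14 + 21) + 84 = 231. Formula = 112 + 56 + 84 = 252. Ratio = 231/252 = 91.7%. Tables 14-4 and 14-5 show this pattern for DT 20 to 10 mg/kg at 16-18 kg and for granules 14 to 7 mg/kg at 17-19 kg, with no new strength needed.

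The reverse change, 1 unit to 2 on the same day, gives consumed 56 + (7 + 42) + 168 = 273 and formula 56 + 28 + 168 = 252, a ratio of 108.3%. Where new strengths must be dispensed, that contact may open a new period; the SAP does not say.

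Some changes leave the total untouched. At 25 kg, DT at 20 and at 10 mg/kg is one tablet a day (500 mg, then 250 mg). Counts by strength go wrong but their sum does not. A change made at a counting visit and kept until the next is also scored correctly.

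**Arm level (assumption: 14-day within-period holds, frequency differing by 5 to 20 percentage points between arms; the documents give no rates).** Shift = frequency difference × 14/168, which is 0.42 to 1.67 points. The standard error of the arm difference is 17.625 × √(2/45) = 3.72, so the shift is 0.11 to 0.45 of it.

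**Equal frequency (assumption: 10% to 30% in both arms).** SD = √(17.625² + p(1 − p) × 8.33²) = 17.80 at 10% and 18.03 at 30%. Power falls from 84.7% to 84.1% and 83.3%, at most 1.4 points. The loss is smaller if 17.625 already contains this variation.

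**Period length.** If Amendment 3 periods end the day before the next visit, the added day gives 28 days, as in the End-of-Core SAP. If they end on the visit date, it gives 29, and a perfect taker scores 168/(6 × 29) = 168/174 = 96.6% in either arm.

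**The case against.** The strongest reply is that the 28-day periods are assumed. Neither SAP defines the visit period. Core visits are weekly for the first three weeks (Protocol 7.1.2). Patients interrupted for an adverse event or abnormal laboratory value are followed at least weekly for four weeks (Protocol 6.2.3), and the End-of-Core SAP closes a period at the next assessment without limiting this to scheduled counting visits. If those contacts count, periods around a hold are short. The programming specifications, which might settle this, are not among the documents, and the body of the core schedule (Table 7-1) was not readable in the copy used. This stands: the shortfalls in the table are upper values for a hold of that length. Shorter periods shrink them, however, only if the prescribed count is recorded as zero during the hold, and the documents do not establish that either.

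Four stronger readings are tempting and should not be drawn:

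- A reader might infer that such patients are classed as non-compliant. The endpoint is a continuous ratio analysed by ANCOVA with no cut-off. The effect is a lowered or raised value.
- A reader might infer that the arm comparison was biased, or that this explains the missed objective. No frequencies by arm are given, so neither size nor direction can be derived.
- A reader might infer ratios of 105% to 115% when a hold covers the first day of a later period. That needs a prescribed count of zero on that day, which the documents do not establish.
- A reader might infer that the two reports used different period lengths. The wording differs, but whether the day counts differ depends on an end date that Amendment 3 does not state.

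It is also fair to say that little now turns on this. The primary analysis is complete and the objective was not met (End-of-Core SAP, Table 1-1), the End-of-Core analysis involves no formal testing, and the final SAP repeats compliance only if data change significantly.

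**Conclusion.** The point holds as a defect in the SAP wording: a stated rule for a co-primary endpoint does not produce the quantity that the same paragraph defines. On 4-weekly periods, one ordered 14-day hold inside a period costs a fully adherent patient up to 8.3 points at 24 weeks, about half the planning SD. At arm level the effect is modest under every assumption tried and of unknown direction. How many reported values were affected cannot be told from the documents. No success claim rested on the variable, but the reported 24- and 48-week compliance estimates do, so a supplementary correction is worth making.

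**What to change.** Keep the pre-specified result as primary, and:

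1. Define the visit period and its end date so that each day is counted once, and state whether the Amendment 3 and End-of-Core rules give the same number of days.
2. Add a labelled supplementary analysis of compliance at 24 and 48 weeks. The prescribed count becomes the sum over days, for each strength, of the count in force that day, with zero on investigator-ordered hold days identified by the recorded reason.
3. Take change dates from the Dose Administration Record and per-strength counts from the prescription and dispensing records. Where dates are incomplete, use the SAP rule for that period and report how often.
4. Show by arm, in ICT-naive patients, how many had a within-period hold or change in the first 24 weeks. The exposure summary in SAP 2.6 does not give this: it covers the whole core phase or granule period and does not place changes within counting periods.

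If the programming specifications already split periods at changes, a sentence saying so would replace steps 2 and 3.

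The cost is re-deriving one variable and merging two data sources. Dose-record dates other than the last dose are not imputed (SAP 4.8.5), so some patients will need the fallback. The corrected denominator also depends on how investigators recorded zero-dose days in an open-label trial, which is why it should stay supplementary. No clinical hold or dose rule is affected.

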### **2.8.2 Statistical hypothesis, model, and method of analysis**

The primary efficacy analysis will be the comparison of means between the two treatment arms of change from baseline after 24 weeks of treatment in serum ferritin and mean relative consumed stick pack /tablet count over 24 weeks of treatment.

The trial will be claimed successful if the superiority of granule formulation relative to DT formulation could be demonstrated with regard to both endpoints. Therefore no adjustment for multiplicity of the type I error (alpha) is required.

The primary inferential analysis described below will be based on the FAS-1.

Let  $\mu_{SF,G}$  and  $\mu_{SF,DT}$  denote the mean change from baseline in Serum Ferritin (SF) to week 25 visit for granule and DT formulations, respectively. Let  $\mu_{C,G}$  and  $\mu_{C,DT}$  be similarly defined for compliance measured by stick pack /tablet count.

The null and the alternative hypothesis are defined as follows:

$H_{0,SF}: \mu_{SF,G} = \mu_{SF,DT}$  no effect of granule formulation with regard to change in SF, and/or

$H_{0,C}: \mu_{C,G} = \mu_{C,DT}$  no effect of granule formulation with regard to compliance

versus

$H_{1,SF}: \mu_{SF,G} < \mu_{SF,DT}$  mean change in SF favorable for granule formulation compared to DT formulation, and

$H_{1,C}: \mu_{C,G} > \mu_{C,DT}$  mean compliance favorable for granule formulation compared to DT formulation

Analysis of covariance (ANCOVA) will be performed for comparison between both treatment groups. The ANCOVA model for compliance endpoint will include treatment group and the age group as per stratification (2 to <10 years versus 10 to <18 years), as factors. The model for serum ferritin endpoint will also include the serum ferritin value at baseline as covariate.

### **2.8.3 Handling of missing values/discontinuations**

In case of missing serum ferritin after 24 weeks of treatment, the last available post-baseline serum ferritin value will be used in the calculation of the primary endpoint. Patients without post-baseline serum ferritin value will be excluded from the analysis.

No imputation will be performed for the compliance endpoint calculation. However, patient who discontinued before the week 25 visit will be included in the compliance endpoint calculation.

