### **7.2.2 Serum Ferritin**

Serum ferritin test will be performed during the core phase at Screening Visits 1 and 2 (in the absence of infection) to assess the eligibility of the patient. The baseline serum ferritin value is defined as the average of the two measurements obtained during the screening period. Thereafter serum ferritin testing will be performed at weeks 5, 9, 13, 17, 21, 25, 29, 33, 37, 41, 45 and EOT(core)/777 visits to evaluate the clinical benefit related to improved compliance of the new formulation. This will be done monthly as per Exjade prescribing information during

the extension phase. A central laboratory will be used for analysis of all specimens collected.  

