## 2.8.4 Supportive analyses

The following supportive analyses will be provided:

- The primary analysis as described in [Section 2.8.2 & Section 2.8.3](#) will be also performed for the PPS, FAS-2 and FAS-3 as supportive efficacy analyses;
- In addition, descriptive summaries will be provided for the FAS-1 by treatment arm:
  - Summary of absolute and relative change from baseline values in serum ferritin assessed at week 25 visit and 95% confidence intervals for means (see [Table 4-2](#) for time window definition);
  - Summary statistics of overall compliance measured by stick pack/tablet count assessed at week 25 visit and 95% confidence intervals for means. Patient who discontinued before the week 25 visit will be included in the compliance endpoint calculation.

These descriptive analyses will be repeated by the age stratification factor, by average actual daily dose category, by baseline serum ferritin category, and underlying disease (see [Table 2-6](#)).

- A forest plot of mean difference between treatments will be presented with absolute change in serum ferritin after 24 weeks of treatment and the corresponding exact 95%CI including these subgroups. Point estimates and 95% CI will be generated.
- If more than 10% of patients have no serum ferritin value after 24 weeks of treatment, sensitivity analysis will be performed for the primary analysis for serum ferritin using multiple imputation method. This analysis will be performed for the FAS-1.

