## 2.11 Sample size

The primary objective of this study is to evaluate patient compliance (using stick packs or tablet counts) and change in serum ferritin over time for both formulations of deferasirox in pediatric ICT naïve patients with iron overload.

The sample size was estimated to demonstrate superiority and statistical significance for both co-primary endpoints.

The assumptions made for this study were:

- For serum ferritin:  
An expected improvement between both formulations in serum ferritin change from baseline after 24 weeks of treatment of -450ng/mL with a standard deviation (SD) of 900 ng/mL based on results from study CICL670A0107 in pediatric patients treated with Exjade on ≥ 25 mg/kg/day after 24 weeks of treatment
- For compliance using stick packs or tablets counts:  
An expected improvement between both formulations in mean relative consumed tablet count of 10% with a SD equal to 17.625% based on the pooled analysis on pediatric patients (n=77) from Exjade studies [[ICL670A2206](#)] (n=39), [[ICL670A2204](#)] (n=24) and [[ICL670A2214](#)] (14).

The sample size, driven by the calculation of serum ferritin, has been determined to obtain 76% power at a one-sided 5% level of significance for showing superiority of granule formulation over DT formulation with respect to change from baseline after 24 s of treatment in serum ferritin.

A sample size of 45 in each group will have 76% power to detect a difference in means of 450 ng/mL assuming that the common SD is 900 ng/mL using a two group t-test with a 0.050 one-sided significance level. With 45 patients per arm, the power to detect a difference of 10% or more in mean compliance is about 84%.

Considering a potential of 5% dropout rate patients, the required sample size to achieve the primary objective is 48 chelation naïve patients for each treatment group (96 patients in total).

In addition, the clinical trial will enroll patients previously treated with iron chelation patients. Considering that a direct comparison of granule and DT formulations in terms of efficacy is not foreseen in previously chelated patients, the required sample size is not based on power calculations as usual. The selection of number of patients is based on the precision in the estimate of SF change at 48 weeks of treatment and on practical considerations.

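### A missing week-25 ferritin is carried forward, and the only alternative missing-data analysis of the treatment comparison is not expected to run at the planned 5% dropout

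*SAP*

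**What the plan says.** **Primary rule.** SAP 2.8.3 states that, for a missing 24-week ferritin, "the last available post-baseline serum ferritin value will be used in the calculation of the primary endpoint". Patients with no post-baseline ferritin are excluded. Protocol 10.4.3 says the same.

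**Data available.** Protocol 7.2.2 provides that "serum ferritin testing will be performed at weeks 5, 9, 13, 17, 21, 25" and then every four weeks to the end of the core phase. The ANCOVA in SAP 2.8.2 uses treatment, age group, baseline ferritin and a single post-baseline value.

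**Alternative analysis.** SAP 2.8.4 reads: "If more than 10% of patients have no serum ferritin value after 24 weeks of treatment, sensitivity analysis will be performed", by multiple imputation on the FAS-1. SAP 4.6.1 repeats the condition and names the SAS procedure but gives no imputation model. Protocol 10.4.4 has the same 10% threshold. The repeats on the PPS, FAS-2 and FAS-3 refer back to SAP 2.8.3, so they also carry values forward.

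**What is unconditional.** SAP 2.8.4 plans a by-arm summary of week-25 change with 95% confidence intervals and a forest plot of mean differences. It states no missing-data method for either. The interim analysis (SAP 2.12) plans a descriptive multiple-imputation summary with no threshold.

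**Planned loss.** SAP 2.11 sizes the trial "Considering a potential of 5% dropout rate patients", giving 48 chelation-naïve patients per arm. Under Protocol 6.2.2, patients who stop study drug leave the study after their final visit.

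**The concern.** A patient who stops drug early has a final visit and is then withdrawn, so a missing week-25 ferritin is a built-in consequence of stopping. If ferritin is still moving when the patient stops, the carried-forward value understates the 24-week change, and the ANCOVA gives it the same weight and certainty as a measured one.

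This matters most if the arms lose patients at different rates or times. The trial is open-label, and its rationale (Protocol 2.1) is that the dispersible tablet is less palatable and less convenient, so arm-dependent stopping is foreseeable. Carrying forward can then create or hide a difference in a co-primary endpoint. The analysis that could show this is conditional on a missing rate twice the planned dropout. The descriptive interim summary carries no such condition, so the confirmatory comparison has the weaker protection.

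**Working it through.** **1. Reproduce the plan's power.** SAP 2.11: "A sample size of 45 in each group will have 76% power to detect a difference in means of 450 ng/mL". The same section supplies the other inputs used below (SD 900, one-sided 5% test).

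- Two-group one-sided t-test, 45 per arm, difference 450, SD 900: power 76.1%, as stated.
- 45 / 0.95 = 47.4, rounded up to 48 per arm, as stated.
- With all 48 per arm observed, power is 78.4%. The standard error is 900 × √(2/48) = 183.7 ng/mL.

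**2. How often would the imputation run?** More than 10% of 96 is more than 9.6, so at least 10 patients. With X binomial (96, p):

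| Missing rate p | Expected missing | P(X ≥ 10) |
|---|---|---|
| 5% | 4.8 | 2.2% |
| 7.5% | 7.2 | 18% |
| 10% | 9.6 | 50% |
| 12.5% | 12.0 | 78% |
| 15% | 14.4 | 93% |

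Up to 9 of 96 (9.4%) can be carried forward with no alternative missing-data analysis of the comparison.

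**3. Assumptions for the size of the effect.** The documents give no ferritin time course, so these are mine: change is linear over 24 weeks, and last visits are spread evenly over weeks 5, 9, 13, 17 and 21. The fractions of the course completed are 4/24, 8/24, 12/24, 16/24 and 20/24, with mean f = 0.5. An arm with true mean change μ and missing proportion m then has carried-forward mean μ × [1 − m(1 − f)].

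**4. Balanced 5% dropout.**

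- f = 0.5: 450 × (1 − 0.05 × 0.5) = 439 ng/mL. The loss of 11 ng/mL is 0.06 standard errors, and power at 48 per arm is 76.6%.
- All last seen at week 5 (f = 1/6): 431 ng/mL, power 75.4%.
- All last seen at week 21 (f = 5/6): 446 ng/mL, power 77.8%.

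**5. Lopsided dropout below the trigger, no true difference.** Assume a change of -500 ng/mL in both arms and SD 900. The false difference is 500 × (excess losses / 48) × (1 − f). The one-sided error is 1 − Φ(1.645 − false difference / 183.7), when the loss is in the tablet arm.

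| Excess losses in one arm | f | False difference (ng/mL) | One-sided error |
|---|---|---|---|
| 5 (for example 5 v 0, or 7 v 2) | 0.5 | 500 × 5/48 × 0.5 = 26 | 1 − Φ(1.503) = 6.6% |
| 9 (9 v 0) | 0.5 | 500 × 9/48 × 0.5 = 47 | 1 − Φ(1.390) = 8% |
| 9 (9 v 0) | 1/6 | 500 × 9/48 × 5/6 = 78 | 1 − Φ(1.220) = 11% |

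If ferritin falls, the arm with fewer losses is favoured. If it rises, the sign reverses.

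**6. The same with a true difference of -450.** Assume -300 on tablets, -750 on granules and f = 0.5. Nine losses on tablets give -750 + 300 × 0.906 = -478. Nine losses on granules give -750 × 0.906 + 300 = -380. The estimate can therefore move either way.

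**The case against.** Several points on the other side stand.

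- **A reader might infer that ferritin has no missing-data check at all.** The documents do not support that. The week-25 summary and forest plot in SAP 2.8.4 are unconditional. If they use only values inside the time window of SAP Table 4-2, they give an observed-case comparison to set beside the primary result. They are descriptive, however, and state no rule for missing values.
- **A reader might infer that carrying forward does serious damage at the planned dropout.** It does not. Balanced 5% dropout costs about 11 ng/mL and under two points of power, toward no difference. At 15% missing or more the effect could be larger, but there the imputation would run with at least 93% probability.
- **A reader might infer that the imputation is certain to be off.** The trigger counts missing ferritin values, not dropouts. Missed samples in continuing patients also count, so not running is an expectation.
- **A linear course is not documented.** The linear relation in Protocol 2.2 is between the 24-week and 48-week changes, not over time within 24 weeks. Protocol 6.1.1 also allows dose changes for ferritin in naïve patients after 4 weeks. A statement such as a third of the change being reached by week 9 is therefore an assumption.
- **A repeated-measures model is not plainly the right primary analysis.** It is unbiased when missingness depends on observed data. Children who refuse the drug for its taste may not fit that. It also estimates ferritin as if those who stopped had continued, which is a different question in a trial about whether children keep taking the drug.

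What survives is moderate, lopsided missingness below the threshold, where the plan guarantees no alternative analysis of the treatment comparison.

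**Conclusion.** The point holds as a gap in sensitivity analysis, not as a demonstrated bias in the result. The carry-forward rule and the 10% condition are explicit in both documents. At 5% missing, the chance that the imputation runs is about 2%, assuming 96 patients and independent missingness.

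The likely effect is small if the arms lose patients alike. It is moderate in the unfavourable case below the trigger: a false difference of about 47 ng/mL (0.26 standard errors), or 78 ng/mL (0.43 standard errors) if every loss is at week 5. Those figures rest on the linear course, the spread of last visits, the -500 ng/mL change and all nine losses falling in one arm. They scale with the assumed change. The 8% and 11% errors apply to the ferritin test alone; a success claim also needs the compliance endpoint.

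Table 1-1 of the End of Core Phase SAP records that the primary objective was not met, so a false claim of success is no longer the live issue. Interpretation of the ferritin estimate is, since carrying forward could equally have shrunk a difference. That SAP keeps the carry-forward rule (2.8.3) and does not repeat the supportive analyses (2.8.4).

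**What to change.** 1. Delete the 10% condition in SAP 2.8.4, SAP 4.6.1 and Protocol 10.4.4. Always run the FAS-1 multiple-imputation analysis, with a stated model that includes the intermediate ferritin visits, treatment, age group and baseline ferritin.
2. Add a repeated-measures model of the week 5 to week 25 changes, with treatment, visit, treatment by visit, age group and baseline ferritin, and read the contrast at week 25. Present it beside the carry-forward ANCOVA. It could replace that analysis as primary only if the sponsor wants the effect as if patients had continued treatment.
3. State the missing-data rule for the week-25 summary and forest plot, and tabulate missing week-25 values by arm and last ferritin visit. That table would show how far the lopsided case applies.

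The primary analysis has been run, so items 1 and 2 should now be reported as labelled post hoc sensitivity analyses. No new data or patients are needed. The cost is programming and a somewhat larger standard error, since missing values no longer count as observed; that is a real price in a design with 76% power.
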